8.2.3.2 MI-MCMC / Reference-based imputation

Deviations from the missing at random pattern will be evaluated using a reference-based MI approach (see Section 4.2.2.2). Intermittent missing data will be imputed using the MCMC method. The remaining monotone missing data will be assumed to follow a missing not at random pattern. These data will be imputed using a reference-based approach in which the MI model is based on data from the placebo group, thereby assuming that monotone missing data follow a trajectory similar to the placebo group.

The same analysis model as in the primary efficacy analyses will then be used on the imputed data set.

8.2.3.3 Tipping point analysis

Tipping point analyses will be performed to evaluate missingness assumptions. Various delta adjustments will be made to the assumed responses on the monotone missing data in each treatment group independently with various degrees of plausibility. It will include scenarios where study participants who have missing data and are randomized to bimekizumab have a

lower probability of response compared to study participants who have missing data and were randomized to placebo. This includes the worst-case scenario where study participants who have missing data and are randomized to bimekizumab are considered nonresponders, while study participants who have missing data and were randomized to placebo are considered responders. The goal of the tipping point analysis is to systematically vary assumptions until there is no evidence of a treatment effect (if possible). The plausibility of such required delta adjustment will then be assessed.

Refer to Section 4.2.2 for more details on the methodology.

8.2.3.4 Treatment policy

The treatment policy strategy for addressing intercurrent events will be considered. This will be based on an analysis of all available data at Week 16 regardless of the occurrence of intercurrent events. This analysis will use the same models specified for the primary analysis, where study participants are analyzed according to their randomized treatment, even if they discontinued study treatment for any reason prior to Week 16. Even though efforts will be made to collect the primary outcome data for all study participants at Week 16, there may still be some study participants for whom Week 16 efficacy data cannot be obtained. In this case, missing data will be imputed using multiple imputation under the assumption of MAR (see Section 4.2.2). The same analysis model as in the primary efficacy analyses will then be used on the imputed data set and the resulting inferential statistics will then be combined into a single inference using Rubin's rule.

8.2.3.5 Analysis on observed cases

An additional supportive analysis will be based on observed data only for study participants with a lesion count assessment at Week 16 who have not had an intercurrent event on or before Week 16. Study participants with missing data at Week 16 will be treated as missing (see Section 4.2.2).

The same analysis model as in the primary efficacy analyses will then be used on the imputed data set.

8.2.3.6 Analysis on FAS

The primary efficacy analyses from Section 8.2.2 will be repeated based on the FAS.

8.2.3.7 Analysis on PPS

The primary efficacy analyses from Section 8.2.2 will be repeated based on the PPS.

8.2.3.8 Analysis on CFS

The primary efficacy analyses from Section 8.2.2 will be repeated based on the CFS.

8.2.3.9 Analysis including COVID-19 impact as intercurrent event

An additional sensitivity analysis will include an additional intercurrent event. The composite estimand combines the clinically meaningful improvement from Baseline based on the HiSCR₅₀ response and completion of study treatment through Week 16 without receiving systemic antibiotic rescue medication or discontinuing IMP due to an AE or lack of efficacy.

The following 4 attributes describe the estimand that will be used to define the treatment effect of interest for this sensitivity efficacy analysis:

1. Population=Study participants meeting the protocol-specified inclusion/exclusion criteria.
2. Study participant-level outcome=HiSCR₅₀ at Week 16.
3. Intercurrent event handling=An intercurrent event is defined as receipt of systemic antibiotic rescue medication, discontinuation of study treatment due to an AE or lack of efficacy prior to Week 16, or missing data due to COVID-19. More information is provided in Section 3.9. A composite strategy will be implemented in which a positive clinical outcome is defined as achieving HiSCR₅₀ at Week 16 and not receiving systemic antibiotic rescue medication, not discontinuing study treatment due to an AE or lack of efficacy through Week 16, and not having missing data due to COVID-19. Any missing data at Week 16 that are not preceded by an intercurrent event will be imputed using multiple imputation as defined in Section 4.2.1.
4. Population-level summary measure=conditional odds ratio comparing bimekizumab to placebo adjusted for stratification factors used in the randomization.

The same imputation techniques and analysis model as in the primary efficacy analyses will then be used.

8.2.3.10 Cochran-Mantel-Haenszel test

The primary efficacy analyses from Section 8.2.2 will be repeated where the CMH test with fixed effects for treatment, Hurley stage at Baseline, and Baseline antibiotic use will be used as stratification variables. Pairwise treatment comparisons will be made based on the CMH test using the p-value for the general association. The odds ratio and associated confidence interval (CI) based on the Wald test will be provided.

8.2.3.11 Center-by-Treatment Interaction

The center-by-treatment interaction will be tested by adding center and a center-by-treatment interaction term in the logistic regression model described in Section 8.2.2. In the model, center will be based on the original centers prior to pooling. However, if the model is unable to converge due to a low number of participants at a given center, a pooling (see Section 3.7) will be described in order to allow the model to converge. In order to obtain reasonable estimates of variability for a treatment arm at a given center, a minimum of 21 participants will be considered acceptable for a center to be included in the model without pooling. Given the 2:2:2:1 randomization allocation scheme, this should provide a minimum of about 12 participants in the bimekizumab [REDACTED] treatment group, 6 participants in the bimekizumab [REDACTED] treatment group, and 3 participants in the placebo treatment group. Centers with fewer than 21 participants will be eligible for pooling. The pooling algorithm used is described in Section 3.7.

In order to achieve model convergence, other explanatory variables eg, Baseline Hurley Stage and Baseline antibiotic use may be dropped from the model. If model convergence is still not achieved, region and a region-by-treatment interaction term will be added to the model instead. Regions are defined in Section 3.7.

If the center-by-treatment interaction is not found to be significant ($\alpha=0.05$), then no further analyses will be performed. On the other hand, if the interaction is significant, further analyses

will be conducted to determine which center or centers may be the source of interaction. This will be done by running the logistic regression model (including the interaction term) where each center will be systematically removed from the model. This impact of a given center will be based on the change in the interaction p-value when that center is removed. The center or centers that appear to be driving the significant interaction effect will then be removed from the model to verify that conclusions remain the same with or without the influential center(s). This sensitivity analysis will be based on RS with MI/MCMC Monotone Regression for missing data.

8.3 Secondary efficacy endpoints

The secondary efficacy analyses will be performed based on the RS. Sensitivity analyses of the secondary endpoints will be performed on the CFS.

Missing data handling and sensitivity analyses of the secondary efficacy endpoints are described in Section 4.2.1.2.

The analyses of the secondary endpoints are summarized in Table 8–2 .

Table 8–2: Estimand Details and Attributes for Secondary Analyses

Objective Clinical Category	Statistical Category (Section)	Estimands for Secondary Endpoints			PLS (Analysis)
		Variable/Endpoint	Pop	IES	
Secondary Objective: Evaluate the efficacy of bimekizumab on other measures of disease activity in study participants with moderate to severe HS					
HiSCR ₇₅	Secondary (Section 8.3.1)	HiSCR ₇₅ response at Week 16	RS	Composite strategy, as for the primary analysis.	The odds ratio versus placebo based on a logistic regression, as for the primary analysis.

Table 8–2: Estimand Details and Attributes for Secondary Analyses

Objective Clinical Category	Statistical Category (Section)	Estimands for Secondary Endpoints			PLS (Analysis)
		Variable/Endpoint	Pop	IES	
Flare	Secondary (Section 8.3.2)	Flare by Week 16	RS	The main intercurrent events are receipt of systemic antibiotic rescue medication or discontinuation of study treatment due to an AE or lack of efficacy prior to Week 16. A composite strategy will be used, ie, the occurrence of an intercurrent event will be handled by evaluating the corresponding participants as treatment failures (flare).	The odds ratio versus placebo based on a logistic regression, as for the primary analysis.
DLQI	Secondary (Section 8.3.3.1)	Change from Baseline in DLQI total score to Week 16	RS	The main intercurrent events are receipt of systemic antibiotic rescue medication or discontinuation of study treatment due to an AE or lack of efficacy prior to Week 16. The intercurrent events will be handled using a hypothetical strategy , whereby all data at and after the intercurrent event will be treated as missing.	Difference in mean change from Baseline (LSMD from ANCOVA) to Week 16 in the DLQI total score for participants receiving bimekizumab versus placebo. Missing values will be imputed using MI – MCMC/Monotone Regression under a missing at random assumption.

Table 8–2: Estimand Details and Attributes for Secondary Analyses

Objective Clinical Category	Statistical Category (Section)	Estimands for Secondary Endpoints			PLS (Analysis)
		Variable/Endpoint	Pop	IES	
DLQI	Secondary - Sensitivity (Section 8.3.3.2)	Change from Baseline in DLQI total score to Week 16	RS	The main intercurrent events are receipt of systemic antibiotic rescue medication or discontinuation of study treatment due to an AE or lack of efficacy prior to Week 16. The intercurrent events will be handled using a while on treatment strategy , whereby only participants with a DLQI total score at Week 16 who have not had an intercurrent event on or before Week 16 are included.	Difference in mean change from Baseline (LSMD from ANCOVA) to Week 16 in the DLQI total score for participants receiving bimekizumab versus placebo. Missing values will not be imputed.
HSSDD	Secondary (Section 8.3.4.1)	Change from Baseline in worst skin pain score, as assessed by “worst skin pain” item in HSSDD to Week 16	RS	The main intercurrent events are receipt of systemic antibiotic rescue medication or discontinuation of study treatment due to an AE or lack of efficacy prior to Week 16. The intercurrent events will be handled using a hypothetical strategy , whereby all data at and after the intercurrent event will be treated as missing.	Difference in mean change from Baseline (LSMD from ANCOVA) to Week 16 in the worst skin pain score for participants receiving bimekizumab versus placebo. Missing values will be imputed using MI – MCMC/Monotone Regression under a missing at random assumption.

Table 8–2: Estimand Details and Attributes for Secondary Analyses

Objective Clinical Category	Statistical Category (Section)	Estimands for Secondary Endpoints			PLS (Analysis)
		Variable/Endpoint	Pop	IES	
HSSDD	Secondary (Section 8.3.4.2)	Change from Baseline in worst skin pain score, as assessed by “worst skin pain” item in HSSDD to Week 16	RS	The main intercurrent events are receipt of systemic antibiotic rescue medication or discontinuation of study treatment due to an AE or lack of efficacy prior to Week 16. The intercurrent events will be handled using a while on treatment strategy , whereby only participants with a HSSDD worst skin pain score at Week 16 who have not had an intercurrent event on or before Week 16 are included.	Difference in mean change from Baseline (LSMD from ANCOVA) to Week 16 in the worst skin pain score for participants receiving bimekizumab versus placebo. Missing values will not be imputed.
HSSDD	Secondary (Section 8.3.5.1)	Skin pain response at Week 16, as assessed by the “worst skin pain” item in the HSSDD, defined as an improvement in the weekly worst skin pain score of at least 3 points	RS ^a	Composite strategy , as for the primary analysis.	The odds ratio versus placebo based on a logistic regression, as for the primary analysis.

Table 8–2: Estimand Details and Attributes for Secondary Analyses

Objective Clinical Category	Statistical Category (Section)	Estimands for Secondary Endpoints			PLS (Analysis)
		Variable/Endpoint	Pop	IES	
HSSDD	Secondary Sensitivity (Section 8.3.5.2.1)	Skin pain response at Week 16, as assessed by the “worst skin pain” item in the HSSDD, defined as an improvement in the weekly worst skin pain score of at least 3 points	RS ^a	Composite strategy , as for the primary analysis where the occurrence of an intercurrent event will be handled by evaluating the corresponding participants as nonresponders.	The odds ratio versus placebo based on a logistic regression. Missing values for any other reason will also be imputed as nonresponders.
HSSDD	Secondary Sensitivity (Section 8.3.5.2.2)	Skin pain response at Week 16, as assessed by the “worst skin pain” item in the HSSDD, defined as an improvement in the weekly worst skin pain score of at least 3 points	RS ^a	The main intercurrent events are receipt of systemic antibiotic rescue medication or discontinuation of study treatment due to an AE or lack of efficacy prior to Week 16. The intercurrent events will be handled using a while on treatment strategy , whereby only participants with a HSSDD worst skin pain score at Week 16 who have not had an intercurrent event on or before Week 16 are included.	The odds ratio versus placebo is based on a logistic regression. Missing values will not be imputed.

AE=adverse event; ANCOVA=analysis of covariance; DLQI=Dermatology Life Quality Index; HiSCR=Hidradenitis Suppurativa Clinical Response; HSSDD=Hidradenitis Suppurativa Symptom Daily Diary; IES=intercurrent event(s) strategy; LSMD=Least Squares Mean Difference; MCMC=Markov Chain Monte Carlo; MI=multiple imputation; PLS=Population-level summary; Pop=Population; RS=Randomized Set

^a Analysis includes all study participants in the RS with a Baseline HSSDD Worst Skin Pain score of 3 or higher.

8.3.1 HiSCR₇₅ at Week 16

A categorical response variable, HiSCR₇₅ at Week 16 is defined to be equal to 1 if % Δ AN is less than or equal to -75%, and the change from Baseline in the abscess count is zero or negative (ie, non-positive) together with a non-positive change from Baseline in the draining tunnel (fistula/sinus tract) count, and 0 otherwise. This definition is introduced for identifying participants who respond to the treatment (1 = responder, 0 = nonresponder). The definition of percentage improvement from Baseline is given in Section 8.2.1.

For HiSCR₇₅ at Week 16, logistic regression as specified for the primary analysis will be implemented to test for superiority. The same analysis approach as outlined for the primary efficacy endpoint will be applied.

8.3.2 Flare by Week 16

See Section 8.2.1 for the derivation of AN count.

Disease flare by Week 16 is defined as at least a 25% increase in AN count with an absolute increase of ≥ 2 AN relative to Baseline is observed by Week 16. A participant's disease flare status (yes/no) will be determined at each visit.

The number of participants who experience at least 1 disease flare by Week 16 will be analyzed using a logistic regression model including a fixed effect for treatment, Hurley stage at Baseline, and Baseline antibiotic use. The odds ratio versus placebo, p-value (from Wald test), and CI will be calculated. Missing data will be handled as described in Section 4.2.1.2.

8.3.3 Change from Baseline in DLQI Total Score at Week 16

The DLQI is a questionnaire designed for use in adult participants with skin diseases and has been used in patients with HS. This is a validated, quality-of-life questionnaire that covers 6 domains including symptoms and feelings, daily activities, leisure, work and school, personal relationships, and treatment, as assessed over the past week.

The scoring of each answer for the DLQI is as follows:

Table 8–3: Dermatology Life Quality Index

DLQI Scoring	
Response	Score
Very much	3
A lot	2
A little	1
Not at all	0
Not relevant	0
Question unanswered	0
Q7: ‘prevented work or studying’ = yes	3

The DLQI total score is calculated by adding the score of each question. The maximum score is 30, and the minimum score is 0. The higher the score, the more quality of life is impaired.

Meaning of DLQI Total Score

0-1 = no effect at all on patient’s life

2-5 = small effect on patient’s life

6-10 = moderate effect on patient’s life

11-20 = very large effect on patient’s life

21-30 = extremely large effect on patient’s life

This categorization will not be utilized in the analysis.

Because Q7 has a sub-question (referred to as Q7a here) after the leading yes/no question, some clarifying rules for scoring are provided:

- If Q7 is marked as “yes”, a score of 3 is given regardless of the responses to Q7a.
- If Q7 is marked as “no”, “not relevant”, or is missing and Q7a is “A lot”, a score of 2 is given.
- If Q7 is marked as “no”, “not relevant”, or is missing and Q7a is “A little”, a score of 1 is given.
- If Q7 is marked as “no”, “not relevant”, or is missing and Q7a is “Not at all”, a score of 0 is given.
- If Q7 is marked as “no” or “not relevant” and Q7a is missing, a score of 0 is given.
- If Q7 is missing and Q7a is missing, Q7 is considered unanswered (see below for details on how this impacts the DLQI total score).

If 1 question is left unanswered, this is scored 0 and the scores are summed and expressed as usual out of a maximum of 30. If 2 or more questions are left unanswered, the questionnaire is not scored.

Change from Baseline in DLQI total score is defined as Week 16 DLQI total score minus Baseline DLQI total score.

8.3.3.1 Primary analysis of change from Baseline in DLQI Total score at Week 16

Missing data imputation described in Section 4.2.1.2 will be applied.

Change from Baseline in DLQI total score will be presented by treatment group. The analysis model will be based on an ANCOVA with fixed effects of treatment, Hurley Stage at Baseline, Baseline antibiotic use and Baseline value as a covariate. The least square mean (LSM), standard error (SE), and 95% CI for the LSM will be presented by treatment group. For the comparison between placebo and bimekizumab: the difference between the LSM, the associated 97.5% CI for the contrasts, and the corresponding p-value will be presented. If one dose regimen is tested at the 0.05 significance level as determined in Section 4.5, then the confidence interval will be 95% instead of 97.5% for that dose with a corresponding $Z_{\alpha/2}$ of 1.96. Estimand and intercurrent event details are specified in Table 8–2.

8.3.3.2 Sensitivity analysis of change from Baseline in DLQI Total score at Week 16

A sensitivity analysis using the same analysis model as in Section 8.3.3.1 will be used, based on observed data. Estimand and intercurrent event details are specified in Table 8–2.

8.3.4 Change from Baseline in Skin Pain score at Week 16, as assessed by the “worst skin pain” item in the HSSDD

The items on the HSSDD assess patients’ perception of the core symptoms of HS experienced in the past 24 hours: pain, smell or odor, drainage or oozing from HS lesions, and itch on an 11-point numeric rating scale (NRS). Two items assess skin pain: worst skin pain and average skin pain.

Weekly averages will be derived for each of the items of the HSSDD for weeks matching the post-Baseline dosing weeks up to Week 16. A weekly average is the sum of the scored item over the course of the study week divided by the number of days on which the item was completed. The weekly averages will be relative to the respective visit date except for Baseline, which will be anchored to the first dose of study drug. A weekly average will only be calculated if at least 4 non-missing values (not necessarily consecutive) are available. Otherwise, the HSSDD weekly average for the given question will be set to missing.

Baseline will be computed as the average from the first 7 consecutive day period in which there are at least 4 non-missing entries. That is, first consider the first 7 consecutive days prior to the Baseline visit, but not including the Baseline visit day itself. If there are at least 4 non-missing values (not necessarily consecutive), then the Baseline average will be calculated. If there are less than 4 values, the 7 consecutive day period will move one day earlier. If there are at least 4 non-missing values (not necessarily consecutive) in that period, then the Baseline average will be calculated. This will continue until there are at least 4 non-missing values in a 7 consecutive day

period in the 14 days prior to Baseline. If there is no period in which there are at least 4 non-missing entries, then the Baseline value will be set to missing.

Change from Baseline in worst skin pain score is defined as the average Week 16 worst skin pain score minus the Baseline worst skin pain score. Missing data imputation described in Section 4.2.1.2 will be applied to the weekly averages and not to the individual daily PRO data.

8.3.4.1 Primary analysis of change from Baseline in skin pain score at Week 16

Change from Baseline in worst skin pain score will be presented by treatment group. The analysis model will be based on an ANCOVA with fixed effects of treatment, Hurley Stage at Baseline, Baseline antibiotic use, analgesic use (Section 6.4.2) and Baseline value as a covariate.

The LSM, SE, and 95% CI for the LSM will be presented by treatment group. For the comparison between placebo and bimekizumab, the difference between the LSM, the associated 97.5% CI for the contrasts, and the corresponding p-value will be presented. If one dose regimen is tested at the 0.05 significance level as determined in Section 4.5, then the confidence interval will be 95% instead of 97.5% for that dose with a corresponding $Z_{\alpha/2}$ of 1.96.

8.3.4.2 Sensitivity analysis of change from Baseline in skin pain score at Week 16

A sensitivity analysis using the same analysis model as in Section 8.3.4.1 will be used, based on observed data. Estimand and intercurrent event details are specified in Table 8–2.

8.3.5 HSSDD skin pain response at Week 16

The analysis set for the analyses of the skin pain response will be restricted to those study participants in the RS with a Baseline worst skin pain score of 3 or higher. The weekly scores and Baseline score are derived as specified in Section 8.3.4.

8.3.5.1 Primary analysis of skin pain response at Week 16

Skin pain response at Week 16, as assessed by the “worst skin pain” item in the HSSDD, is defined as an improvement in the weekly worst skin pain score of at least 3 points versus Baseline.

The primary analysis will be based on a logistic regression model including a fixed effect for treatment, Hurley stage at Baseline, Baseline antibiotic use, and analgesic use (Section 6.4.2).

The odds ratio versus placebo, p-value (from Wald test), and 97.5% CI will be calculated. If one dose regimen is tested at the 0.05 significance level as determined in Section 4.5, then the confidence interval will be 95% instead of 97.5% for that dose. Missing data will be handled as specified in Section 4.2.1.2. Estimand and intercurrent event details are specified in Table 8–2.

The number and percentage of participants who are pain responders at Week 16 will be summarized by treatment group.

By-participant listings of pain response status will be provided.

8.3.5.2 Sensitivity analyses of Skin Pain Response at Week 16

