2.4 Determination of sample size

A total of 490 study participants will be randomly assigned in a 2:2:2:1 ratio (stratified by Hurley Stage and current antibiotic use) to the following treatment arms:

- Bimekizumab ██████████ during Initial Treatment Period (Weeks 0-16) and Maintenance Treatment (Weeks 16-48) Period, N=140
- Bimekizumab ██████████ during Initial Treatment Period (Weeks 0-16), and Bimekizumab ██████████ during Maintenance Treatment Period (Weeks 16-48), N=140
- Bimekizumab ██████████ during Initial Treatment (Weeks 0-16) and Maintenance Treatment Periods (Weeks 16-48), N=140
- Placebo during Initial Treatment Period (Weeks 0-16), and Bimekizumab ██████████ during Maintenance Treatment Period (Weeks 16-48), N=70

The analysis of the primary efficacy endpoint and secondary efficacy endpoints are based on a comparison of bimekizumab versus placebo at Week 16, with alpha adjustment strategy as indicated in Section 4.5.

The power to detect a statistically significant difference for each of the endpoints are shown in Table 2-1. Notably, with a 2-sided significance level of 0.025, the sample size of 140:70 provides 73% power for detecting at least a difference of 1.5 (bimekizumab ██████████ vs placebo) for the Worst Skin Pain change from Baseline (CFB) endpoint.

Given the high level of power for each of the primary and key secondary endpoints at the 0.025 significance level for the ██████████ comparison (power \geq 0.89), and per the alpha spending strategy, there is a high likelihood that the ██████████ comparison of Worst Skin Pain CFB vs placebo will be allowed to be tested against the 0.05 level of significance. The power for this latter test is 81%. The sample size is thus ultimately driven by the Worst Skin Pain CFB endpoint.

Furthermore, the randomization ratio of 2:2:2:1 has been chosen to provide study participants with a high probability (6/7 ~ 86%) of being randomized to active study drug.

After randomization for this study was complete, an additional endpoint to assess Worst Skin Pain response was included in the sequential testing procedure. This additional endpoint is based on the threshold for clinically meaningful change and is defined as at least a 3 point decrease from Baseline in HSSDD weekly worst skin pain score at Week 16 among study participants with a score of \geq 3 at Baseline. Note that the power calculations reported in Table 2-1 for this

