endpoint are based on the sample size that was initially driven by the Worst Pain CFB endpoint as described above. With a 2-sided significance level of 0.025, the sample size of 104:52 in the subset of participants reporting Baseline HSSDD worst skin pain score at or beyond the threshold for clinically meaningful change (ie, Baseline HSSDD ≥ 3) provides 53% power for detecting a statistically significant difference between bimekizumab [REDACTED] and placebo in the proportion of Worst Pain responders.

Note that the power at the 0.025 level of significance associated with this endpoint for the comparison between bimekizumab [REDACTED] and placebo is 95%. The [REDACTED] comparison of Worst Skin Pain response vs placebo against the 0.05 level of significance is therefore likely, and the power at this significance level is 65%. Given the strength of the power for the bimekizumab [REDACTED] arm vs placebo across endpoints, it is considered acceptable to have a relatively low power for this final endpoint in the testing sequence for the bimekizumab [REDACTED] treatment arm vs placebo.

Table 2–1: Power calculation assumptions and methods

Endpoint	Power $\alpha = 0.025$, 2-sided		Assumptions		
	[REDACTED]	[REDACTED]	Week 16 Bimekizumab [REDACTED] N=280 ^a	Week 16 Bimekizumab [REDACTED] N=140	Week 16 Placebo N=70
HiSCR ₅₀	0.99	0.90	Proportion responders=0.60	Proportion responders=0.50	Proportion responders=0.25
HiSCR ₇₅	0.99	0.98	Proportion responders=0.45	Proportion responders=0.35	Proportion responders=0.10
Flare	0.99	0.99	Proportion of participants with flare by Week 16=0.09	Proportion of participants with flare by Week 16=0.19	Proportion of participants with flare by Week 16=0.52
DLQI	0.99	0.96	Mean CFB=-5.4; SD=6.8	Mean CFB=-4.8; SD=6.8	Mean CFB=-0.8; SD=6.6
Worst Skin Pain CFB ^b	0.89	0.73	Mean CFB=-2.2; SD=3.2	Mean CFB=-2.0; SD=3.2	Mean CFB=-0.5; SD=3.7
Worst Skin Pain Response ^c	0.95	0.53	Proportion responders=0.53	Proportion responders=0.43	Proportion responders=0.23

CFB=change from Baseline; [REDACTED] SD=standard deviation

Note: Estimates for HS0004 are based on Week 12 data from the HS0001 study.

^a Pooled [REDACTED] at Week 16 from [REDACTED] and [REDACTED] arms

^b Within-participant average of Worst Skin Pain according to 24-hour recall.

^c Assumes N=208, 104, 52 in [REDACTED] and placebo, respectively, to account for Worst Skin Pain score at or above 3 (ie, the threshold for clinically meaningful change from Baseline)

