4.5 Multiple comparisons/multiplicity

To control the overall type I error rate at 0.05 for the multiple comparisons in the primary and secondary efficacy endpoints, a closed testing procedure under a parallel gatekeeping framework will be applied (Sun, 2018).

[figure not shown]
Under this framework, each bimekizumab dose of [REDACTED] and [REDACTED] will be compared to placebo in the first instance at a familywise error rate of 0.025 ($\alpha/2$). Simultaneously within each dose, closed testing for the primary and secondary efficacy endpoints will be performed as follows:

1. Step 1: Test HiSCR₅₀ at significance level 0.025.
2. Steps 2 to 6 – If Step 1 is significant at 0.025 then test each secondary endpoint sequentially in the order shown in Figure 4-1, moving to the next step only if significance achieved at 0.025.
3. In the event that Step 6 is significant at 0.025 for a given dose, then Steps 1 to 6 will be repeated for the other dose using a significance level of 0.05.

The secondary efficacy variables supporting the primary efficacy variable are listed below, and will be included in the multiplicity adjustment using the analysis methods specified in Section 8.3:

1. Proportion of study participants who achieve HiSCR₇₅ at Week 16.
 - a. bimekizumab [REDACTED] vs placebo
 - b. bimekizumab [REDACTED] vs placebo
2. Proportion of study participants who experience at least 1 flare by Week 16, with flare defined as a $\geq 25\%$ increase in AN count with an absolute increase in AN count of ≥ 2 relative to Baseline.
 - a. bimekizumab [REDACTED] vs placebo
 - b. bimekizumab [REDACTED] vs placebo
3. Absolute CFB in DLQI Total Score at Week 16.
 - a. bimekizumab [REDACTED] vs placebo
 - b. bimekizumab [REDACTED] vs placebo
4. Absolute CFB in Skin Pain Score at Week 16, as assessed by the “worst skin pain” item (11-point numeric rating scale) in the HSSDD.
 - a. bimekizumab [REDACTED] vs placebo
 - b. bimekizumab [REDACTED] vs placebo
5. Skin pain response at Week 16, based on the threshold for clinically meaningful change (defined as at least a 3 point decrease from Baseline in HSSDD weekly worst skin pain score) at Week 16 among study participants with a score of ≥ 3 at Baseline.
 - a. bimekizumab [REDACTED] vs placebo
 - b. bimekizumab [REDACTED] vs placebo

Figure 4-1: Sequence of testing

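### The worst-skin-pain ANCOVA uses one residual variance, although Table 2-1 plans on unequal SDs; if those SDs hold, a nominal 0.025 test runs at about 0.04

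*SAP*

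**What the plan says.** - **Analysis (SAP 8.3.4.1).** "The analysis model will be based on an ANCOVA with fixed effects of treatment, Hurley Stage at Baseline". The other terms are Baseline antibiotic use, analgesic use and the Baseline value. Differences in least squares means are reported with 97.5% intervals, or 95% where a dose is tested at 0.05. No variance structure is given. The sensitivity analysis in 8.3.4.2 uses the same model on observed data.
- **Planning (SAP 2.4, Table 2-1).** Mean change -2.2 with SD 3.2 (N=280), -2.0 with SD 3.2 (N=140), and for placebo (N=70) "Mean CFB=-0.5; SD=3.7". Stated power at two-sided 0.025 is 0.89 and 0.73. The text adds that "the sample size of 140:70 provides 73% power for detecting at least a difference of 1.5", gives 81% for that comparison at 0.05, and says this endpoint ultimately drives the sample size. A table note says the estimates come from Week 12 of study HS0001.
- **Error control (SAP 4.5).** The procedure is introduced "To control the overall type I error rate at 0.05 for the multiple comparisons in the primary and secondary efficacy endpoints". Each dose starts at 0.025. If all six steps succeed for one dose, "then Steps 1 to 6 will be repeated for the other dose using a significance level of 0.05". Worst skin pain change is the fifth of the six steps.

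**The concern.** An ANCOVA with no other variance structure estimates a single residual variance. With 420 participants on bimekizumab and 70 on placebo, that estimate is set mostly by the active groups. If placebo is the more variable group, as the plan assumes, its contribution to the standard error of each difference is understated, and placebo enters both comparisons. The test then rejects too often when the means are equal, and the interval is too narrow.

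The endpoint sits in the confirmatory sequence, so an understated standard error there bears on the stated error control. The power figures were evidently obtained with separate SDs per group, so the standard error used for sizing is not the one the analysis will use. No planned sensitivity analysis would show the difference.

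**Working it through.** **Inputs (Table 2-1):** SDs 3.2, 3.2 and 3.7; group sizes 280, 140 and 70; mean differences 2.2 - 0.5 = 1.7 and 2.0 - 0.5 = 1.5.

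**1. Reproduce the stated power.** Unequal-variance (Welch) t-test, noncentral t:

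- 280 vs 70: SE = sqrt(3.2²/280 + 3.7²/70) = 0.482; 1.7/0.482 = 3.53; df 96.4; power at 0.025 = 0.893 (stated 0.89).
- 140 vs 70: SE = sqrt(3.2²/140 + 3.7²/70) = 0.518; 1.5/0.518 = 2.89; df 121.8; power at 0.025 = 0.733 (stated 0.73). At 0.05 it is 0.819 (stated 81%, which agrees if truncated).

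A variance pooled over the two compared groups gives 0.945 and 0.782. Pooled over all three it gives 0.950 and 0.813. SD 3.7 throughout gives 0.884 and 0.701. None of these matches both stated figures.

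**2. Standard error under one residual variance, all arms in one model.**

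s² = (279×3.2² + 139×3.2² + 69×3.7²)/487 = 10.73, so s = 3.275.

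| Comparison | Model SE = s×sqrt(1/n + 1/70) | SE under the planning SDs | Ratio |
|---|---|---|---|
| 280 vs 70 | 0.438 | 0.482 | 0.908 |
| 140 vs 70 | 0.480 | 0.518 | 0.925 |

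**3. Actual size.** Size = 2×(1 - Φ(z × ratio)), with z = 2.2414 for 0.025 and 1.96 for 0.05.

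- 280 vs 70: 2.2414 × 0.908 = 2.036, giving 0.042. Nominal 0.05 becomes 0.075.
- 140 vs 70: 2.2414 × 0.925 = 2.073, giving 0.038. Nominal 0.05 becomes 0.070.
- Coverage of the nominal 97.5% interval is 1 - 0.042 = 95.8% and 1 - 0.038 = 96.2%.

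**4. Check by simulation.** The full ANCOVA was simulated 40,000 times without imputation, with assumed covariate distributions and residual SDs of 3.2 and 3.7. At nominal 0.025 it rejects at 0.042 and 0.037 with ordinary standard errors, and at 0.026 for both comparisons with HC3. At nominal 0.05 the rates are 0.074 and 0.068 with ordinary errors, and 0.051 and 0.048 with HC3.

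**5. Range at nominal 0.025 (280 vs 70; 140 vs 70).**

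- Each dose fitted with placebo alone: 0.040; 0.033.
- Placebo SD 3.45: 0.033; 0.031.
- Equal SDs: 0.025 for both.
- Placebo SD 3.0: about 0.02 for both, so conservative.
- Baseline value removing the same absolute variance in every arm (assumed 25% of the active-arm variance; 20,000 simulated trials): 0.046; 0.043. If it removes the same proportion in every arm, step 3 is unchanged.
- DLQI (SDs 6.8, 6.8 and 6.6): 0.022; 0.023.

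**The case against.** The strongest reply is that the SDs are planning values. They describe raw change at Week 12 of another study, whereas the ANCOVA uses residuals at Week 16 of this one. The SAP does not give that study's sample size. If it had 30, 70 or 100 per arm (assumed), 3.7 against 3.2 would give a two-sided F-test p-value of 0.44, 0.23 or 0.15. Equal SDs are therefore not ruled out, and with equal SDs nothing is wrong. This stands, and it makes the finding conditional.

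Four further points have weight:

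- **Which null.** The excess needs equal means with unequal variances. If bimekizumab did nothing at all to pain, the arms would share one distribution and the test would hold its level. The loss of interval coverage does not depend on the means being equal.
- **Which model.** The SAP does not say whether one model covers all arms. Separate fits reduce the excess, mainly for 140 vs 70, without removing it.
- **Imputation.** Section 4.2.2.1 imputes each treatment group separately by default, so the between-imputation variance reflects each arm's own spread. A rough approximation with no auxiliary information and 20% imputed on placebo, 10% on active (assumed) lowers 0.042 and 0.038 to 0.038 and 0.035. At 40% and 20% it gives 0.034 and 0.033.
- **No stated contradiction.** The SAP never asserts equal variances. Powering with separate SDs and analysing by ordinary ANCOVA is common, and here the stated power is the cautious figure.

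A reader might infer that the confirmatory pain tests do run at 0.04, or that the 5% familywise claim in section 4.5 fails. The document does not support either as fact: it contains no variance estimate from this trial. Nor does the point reach the primary endpoint or the three secondary endpoints tested before pain.

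**Conclusion.** The concern holds in conditional form. Section 8.3.4.1 implies one residual variance for an endpoint that the plan itself sized with unequal ones. Under the planning SDs the model standard error is about 7-9% too small with all arms in one model. A nominal 0.025 test of equal means then runs at 0.038-0.042 (0.033-0.040 if each dose is fitted with placebo alone), and the nominal 97.5% interval covers about 96%.

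This rests on the residual SDs keeping the 3.2 to 3.7 ratio and on the group sizes being as planned; multiple imputation was not simulated. At a placebo SD of 3.45 the size is about 0.03, and at equal SDs it is 0.025. It is worth correcting because the test is confirmatory, the plan's only variance figures point this way, and a method that needs no equal-variance assumption is readily available. DLQI shows no such problem; its tests would be slightly conservative.

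**What to change.** In section 8.3.4.1, for worst skin pain change only, keep the ANCOVA mean model as written and add one sentence on the variance. Either fit treatment-specific residual variances with Satterthwaite or Kenward-Roger degrees of freedom (in SAS, PROC MIXED with REPEATED / GROUP=treatment), or use HC3 standard errors. Apply the choice within each imputed data set, before Rubin's rules. Section 8.3.4.2 inherits it, since it uses the same model. Leave the DLQI analysis unchanged.

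The cost is one sentence and a code option. If the planning SDs hold, the interval widens by about 8-10% (1/0.925 = 1.08; 1/0.908 = 1.10). If the SDs are equal it hardly changes. The method then matches the one that reproduces the stated powers of 0.89 and 0.73.
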